## **OBJECTIVES:**

To assess the incidence of perineal pain in postpartum patients 1 week after obstetric anal sphincter injuries (OASIS).

We hypothesize that perineal pain at 1 week postpartum will be reduced by the administration of epidural morphine with or without intravenous ketamine after OASIS compared to on-demand analgesic management.

## **BACKGROUND:**

Obstetric anal sphincter injuries (OASIS) encompass both third and fourth degree perineal tears. These tears can have a significant impact on women's quality of life in the short and long term. One of the most distressing immediate complications of this severe perineal injury is perineal pain. A study by Macarthur et al. revealed that the frequency of perineal pain for patients with OASIS was 100%, 91%, and 20% on day 1, day 7, and 6 weeks' postpartum, respectively. Perineal pain can lead to urinary retention, defecation problems, and postpartum depression in the immediate postpartum period. In the long term, women with perineal pain may have dyspareunia and altered sexual function.

Severity of acute pain after childbirth predicts not only persistent pain, but also postpartum depression. Using a Present Pain Intensity (PPI) scale, Macarthur et al. confirmed that on postpartum day 1, women with OASIS were more likely to use the words "distressing" or "worse" to describe their perineal pain compared to women with intact perineum (48% vs. 13%). Unfortunately, the recommendations for the analgesic management of women with OASIS has not been differentiated from women that undergo vaginal delivery with no trauma or lesser trauma (first and second degree perineal lacerations).

Epidural morphine has long been used for the analgesic management of patients after cesarean delivery, and has also been reported to reduce the need for oral pain medication in the first 24 hours following vaginal delivery. Ketamine, an N-methyl-D-aspartate (NMDA) and glutamate receptor antagonist that decreases central sensitization and pain memory, has also been used at low-doses for multimodal analgesic management of women after cesarean delivery. In a study by Bauchat et al., women who received ketamine reported lower pain score 2-weeks postpartum. Ketamine also has been described as having antidepressant and anti-inflammatory effects, which could mitigate the risk of postpartum depression and improve analgesia in this subset of patients.

We propose a randomized controlled trial to study the effects of three interventions (placebo, low dose intravenous ketamine plus epidural morphine, or epidural morphine alone) in women with OASIS, on acute and chronic pain as well as on patient centered outcomes.

## **INCLUSION AND EXCLUSION CRITERIA:**

Inclusion: age >18 years of age, English-speaking, vaginal delivery (spontaneous or assisted) of a full-term fetus (>37 weeks' gestation), OASIS as assessed by obstetrical provider, functional epidural analgesia at time of delivery, patient amenable to follow-up at their obstetrician's office or at the specialty perineal clinic within the first week postpartum.

Exclusion: previous pelvic surgery, history of chronic pelvic pain, history of recurrent urinary tract infections, women with known malformations of their urinary tract, true allergies to ketamine and/or morphine, preeclampsia or hypertensive disorder at the time of delivery, obstructive sleep apnea.

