**PROCEDURES INVOLVED:**

Prospective, double-blinded, randomized clinical trial.

Randomization: Patients will be approached after repair of OASIS has been completed, and prior to the epidural catheter removal. After informed consent, eligible patients will be randomized to 1 of 3 possible paired interventions:

- 1) Epidural saline + intravenous saline
- 2) Epidural morphine 3mg + intravenous saline
- 3) Epidural morphine 3mg + intravenous ketamine 0.3mg/kg (based on pre-delivery weight)

The subjects will be randomized to a 1/5 chance for group 1 and a 2/5 chance for group 2 and group 3. Randomization and study drug preparation will be conducted by the pharmacy on Prentice 10th floor. The epidural catheter will be removed after study drug or placebo administration, and the patient will be transferred to postpartum unit following standard institutional protocol.

Post-neuraxial morphine order set will be ordered for postpartum analgesia and monitoring.

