## Study timeline:

Version #: 1.5

Version Date:04/23/2019

Page 4 of 14

HRP-593 / v011017

Phase	Sequence of Events	Interventions or Assessment Variables	
I  Information will be collected during patient hospitalization	PPD 0	Checklist followed by study team member for eligibility assessment	Hypothesis testing
	Post-delivery (Following 3 rd stage of labor) Eligibility confirmed, repair of perineal laceration completed, confirmation of hemodynamic stability.	Patient approached by member of study team for informed consent Study drug randomization and administration -Demographics -Obstetrical Data -Anesthesia Data - Richmond Agitation Sedation Score – 15-30 min after intravenous drug administration - Addiction Research Center Inventory and lysergic acid (LSD) questionnaire - Plan to breastfeed. If yes, how long they plan to breastfeed? (<3 months, 3-6 months, >6 months). If multiparous, did they breastfeed in the past? If yes, for how long? When (<3 months, 3-6 months, >6 months) and why did they stop?	
	PPD 1	-Perineal pain scores (VRS) -Need for additional analgesic intake for management of perineal pain (yes or no)  • Total analgesic consumption (opiates/nsaids) - McGill Pain Questionnaire -Brief Pain Inventory (BPI) Short Form	.

II  Information will be collected in-person during patient's perineal clinic visit	PPD 2-7	
 
-Perineal pain scores (VRS)
 
-Need for additional analgesic intake for management of perineal pain (yes or no) 
 
• Total analgesic consumption (opiates/nsaids)
 
 
 
-McGill Pain Questionnaire
 
-Brief Pain Inventory (BPI) Short Form
 
-Edinburgh Postnatal Depression Scale (EPDS)
 
-Maternal Postnatal Attachment Scale (MPAS)
 
- If plan was to breastfeed, is patient currently breastfeeding? yes or no? If not, why did she stop?
 
-MEDoc pathway
 
Hot and Cold Sensory Threshold Assessment test will be performed
 
	
 
-Edinburgh Postnatal Depression Scale (EPDS), Maternal Postnatal Attachment Scale (MPAS): if perineal pain is not well –controlled, the patient will be at increased risk for depression. It will also impact the patient's ability to bond with the newborn.
 
-MEDoc device is predictive of chronic pain
 

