#### **PROVISIONS TO MONITOR THE DATA TO ENSURE THE SAFETY OF PARTICIPANTS:**

A data safety monitoring board consisting of the Department of Anesthesiology Director of Research, a Urology/Gynecology faculty member, and a statistician along with the study research personnel will periodically evaluate the data collected to determine whether participants remain safe. Safety data and adverse event data will be reviewed using the medical record and data collection form. It will be reviewed every 50 subjects or if one of the study subject experiences a rapid response team intervention and review. Data will be compared between groups using the  $\chi^2$  statistic or the Fisher's exact test. A  $P < 0.05$  will be required to reject the null hypothesis.

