**Ketamine:**

Most Frequent: delirium, hallucinations, mood changes, nightmares, tachyarrhythmia, tonic-clonic epilepsy, vocalization

Less Frequent: bradycardia, hypertension, respiratory depression, vomiting, increased intraocular pressure, flashbacks several weeks post operatively

Rare: anaphylaxis, anorexia, diplopia, injection site irritation, laryngismus, nausea, nystagmus, obstructive pulmonary disease, skin inflammation, skin rash

These side effects are uncommon with the lower dose range used in this study.

The risk of the use of the Pathway Pain & sensory evaluation system (Medoc, Dunham, NC) include slight redness on the skin from securing the sensor to the arm with velcro.

There is the risk of the subject becoming emotionally uncomfortable answering some of the surveys' or questionnaires.

Participants are at risk for loss of confidentiality. Strict measures will be in place to ensure that no loss of confidentiality occurs. All participants will be assigned a participant study number that will be used to identify them. One document will link the participant name to their participant number, and this will be kept in a password-protected computer in a locked office in the Prentice Women's Hospital. Only study team members will have access to the study data.

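### No stated exclusion for a history of seizure disorder, psychotic disorder or significant tachyarrhythmia, although the protocol lists related ketamine effects: a minor, cheap safety improvement

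*Combined protocol and SAP*

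**What the plan says.** The exclusion list in INCLUSION AND EXCLUSION CRITERIA covers pelvic surgery, chronic pelvic pain and urinary tract conditions, and ends with "true allergies to ketamine and/or morphine, preeclampsia or hypertensive disorder at the time of delivery, obstructive sleep apnea". It names no neurological, psychiatric or cardiac-rhythm condition.

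Under RISKS TO PARTICIPANTS, the Ketamine entry reads "Most Frequent: delirium, hallucinations, mood changes, nightmares, tachyarrhythmia, tonic-clonic epilepsy, vocalization". It closes with a caveat: "These side effects are uncommon with the lower dose range used in this study".

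On allocation, PROCEDURES INVOLVED states "The subjects will be randomized to a 1/5 chance for group 1 and a 2/5 chance for group 2 and group 3". Group 3 receives ketamine 0.3 mg/kg intravenously with epidural morphine 3 mg.

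Before dosing, the study timeline table gives two relevant steps on the day of delivery: "Checklist followed by study team member for eligibility assessment", with no items listed, and "confirmation of hemodynamic stability". RECRUITMENT METHODS adds that obstetric medical histories are used to find candidates. DRUGS OR DEVICES says that a physician gives the drug and that the anesthesiologist, nurses and research staff do not know the group.

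After dosing, a sedation-agitation score is taken "15-30 min after intravenous drug administration", and the order set schedules respiration checks. Of the safety data, the monitoring section says "It will be reviewed every 50 subjects or if one of the study subject experiences a rapid response team intervention and review". RESOURCES AVAILABLE offers psychiatric support for emergencies that arise.

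**The concern.** The protocol names several neurological, psychiatric and cardiac effects of ketamine, but its eligibility rules do not ask about the corresponding histories. A listed effect need not become an exclusion. Here, however, the drug is given for pain relief, the exclusion would cost very little, and the other described safeguards mostly act after the woman has been exposed.

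Without a written criterion, whether such a woman is enrolled depends on the judgment of whoever screens or treats her. Blinding narrows what that judgment can do. I take the administering physician to be the blinded anesthesiologist. That physician can decline to give the study drug at all, but cannot give the morphine and hold back only the ketamine, because the syringe contents are unknown. A decision made after randomization also costs a randomized participant, which an eligibility rule avoids.

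At stake is the safety of perhaps one woman in the ketamine arm, not the validity of the comparison.

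**Working it through.** **Text check.** The plan gives no figure to reproduce on this point, so the first step sets the listed effects beside the stated safeguards.

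| Ketamine effect in the most frequent tier | Related history | Stated exclusion | Stated pre-dose step that might catch it |
|---|---|---|---|
| Tonic-clonic epilepsy | Seizure disorder | None | None beyond an un-itemised checklist |
| Tachyarrhythmia | Known clinically significant tachyarrhythmia | None | The hemodynamic check could catch an active unstable rhythm, not a history |
| Hallucinations, delirium | Psychotic disorder (inferred) | None | None beyond an un-itemised checklist |

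Hypertension and respiratory depression, by contrast, sit in ketamine's less frequent tier, yet hypertensive disorder and sleep apnea are excluded. The protocol gives no reason for those two exclusions, so reading them as drug-related precautions is my inference. On that reading, conditions matching a lower tier are excluded and those matching the top tier are not. The low-dose caveat does not explain the difference, since it follows all the tiers.

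**Inputs for size.**
- Planned sample: 150 randomized (DATA AND SPECIMEN MANAGEMENT), with recruitment up to 160 (same section and STUDY-WIDE NUMBER OF PARTICIPANTS).
- Ketamine share: 2/5.
- Annual cases of sphincter injury: 327, 281 and 218 (STUDY TIMELINES), with enrollment planned for about one year.
- Combined prevalence p of the three histories: not in the documents. I assume 0.5%, 1% and 2% to show a range.

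**Women assigned ketamine.** 150 × 2/5 = 60; 160 × 2/5 = 64.

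**Expected number of these with one of the histories (arm size × p).**

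| p (assumed) | Of 60 | Of 64 |
|---|---|---|
| 0.5% | 0.30 | 0.32 |
| 1% | 0.60 | 0.64 |
| 2% | 1.20 | 1.28 |

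These are counts of exposure, not of adverse events.

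**Cost of excluding them.**
- Replacements, n/(1 − p) − n: 150/0.995 − 150 = 0.75 at the low end; 160/0.98 − 160 = 3.27 at the high end. So about 1 to 3 women.
- Added enrollment time on 365 days, 365 × (1/(1 − p) − 1): 1.8 days at 0.5% and 7.4 days at 2%.
- Share of a year's cases needed to enroll 160, at 218 cases: 160/218 = 73.4% now; 160/(218 × 0.995) = 73.8% to 160/(218 × 0.98) = 74.9% with the exclusions.
- The same at 327 cases: 160/327 = 48.9% now; 49.2% to 49.9% with them.

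These shares use all cases, before the other eligibility criteria and consent.

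**The case against.** The strongest reply is that the decisive step is not in the documents. They list drug effects; they do not say that women with a related history are at higher risk, and they call none of these histories a contraindication. This stands. The step from effect to exclusion is clinical judgment.

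Second, the choice of conditions is selective. The Ketamine list also includes bradycardia, raised intraocular pressure and obstructive pulmonary disease, and no exclusion is proposed for those. This stands in part. The three proposed items come from the top tier, but the cut is still a judgment. Psychotic disorder is the weakest item, because it is inferred from drug effects and named nowhere in the documents.

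Third, a single low dose with a stated caveat, given by a physician, may be thought protection enough. The section that runs the trial provides care to 90% of obstetric patients, so its staff will often know the patient. This lowers the stakes. But discretion is not a criterion, and blinding prevents selective withholding. The caveat describes participants in general and does not address women with these histories.

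Two stronger readings are tempting and should be resisted. A reader might infer that no one screens for these histories. The documents do not support that: the checklist contents are not given, so the finding is that a screen is not stated, not that it is not done. A reader might also infer from the label of the top tier that seizures or hallucinations are to be expected often in this trial. The protocol says the opposite for this dose.

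**Conclusion.** The concern holds as a minor safety point. The protocol states no exclusion for a history of seizure disorder, psychotic disorder or known clinically significant tachyarrhythmia, and no stated pre-dose step asks about them. Seizure and tachyarrhythmia history rest directly on effects the protocol names; psychotic disorder rests on inference.

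At the assumed prevalence, fewer than one woman in the ketamine arm is affected at 0.5% to 1%, and 1.2 to 1.3 at 2%. The range scales directly with that assumption.

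It would be an overreach to conclude that the trial is unsafe or that participants have been harmed; nothing in the documents shows either. The point does not alter the sample size, the randomization ratio or the primary analysis. It is a cheap improvement, at the level of an optional recommendation.

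**What to change.** Add three items to the exclusion list and to the delivery-day eligibility checklist: (a) history of seizure disorder, (b) history of psychotic disorder, (c) known clinically significant tachyarrhythmia.

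Take them from the medical histories already consulted at recruitment, plus one brief question when the woman is approached, before she consents. The question is needed because the documents do not say whether obstetric histories record psychotic or rhythm disorders. The consent discussion is already planned to take more than 10 minutes, so the added burden is slight.

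Keep women with a mood history eligible: BACKGROUND cites a possible antidepressant effect of ketamine as part of the rationale, and postpartum depression is a secondary endpoint.

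The cost is a protocol amendment, slightly narrower generalizability, and the replacements and few days of enrollment shown in the working. If the sponsor prefers a shorter list, seizure history has the most direct support and should be kept first.

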**STUDY-WIDE NUMBER OF PARTICIPANTS:**

The total number of participants to be accrued with OASIS is 160.

**STUDY-WIDE RECRUITMENT METHODS:** N/A

**MULTI-SITE RESEARCH:** N/A

**STUDY TIMELINES:**

Subjects will be followed within one week of delivery to 12 months postpartum. The incidence of 3rd and 4th degree perineal lacerations at Prentice Woman's Hospital for the last 3 years has been: 327 (YR 2014), 281 (YR 2015), 218 (YR 2016). Therefore, we anticipate to complete enrollment in approximately 1 year, taking into consideration loss to follow-up and recruitment constraints.

**STUDY ENDPOINTS:**

**Primary endpoint:** Perineal pain assessed by verbal rating scale (VRS) in postpartum patients within 1 week after obstetric anal sphincter injuries.

**Secondary endpoints:** Presence of postpartum depression within 1 week after delivery, assessment of maternal-infant bonding, MEDoc Pathway Device pain sensory results within 1 week after delivery, presence of postpartum depression 6 weeks after delivery, perineal pain at 6 weeks after delivery, maternal quality of life 3 months after delivery, and female sexual function 3 months after delivery, perineal pain 3,6, and 12 months after delivery.

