III  Information will be collected remotely via electronic and/or printed surveys, depending on the patient's preference	6 weeks	
 
- Perineal pain scores (VRS)
 
-Need for additional analgesic intake for management of perineal pain (yes or no) 
 
• Total analgesic consumption (opiates/nsaids)
 
 
 
-McGill Pain Questionnaire
 
-Brief Pain Inventory (BPI) Short Form
 
- If plan was to breastfeed, is patient currently breastfeeding? yes or no? If not, why did she stop?
 
-Edinburgh Postnatal Depression Scale (EPDS)
 
-Maternal Postnatal Attachment Scale (MPAS)
 
-Patient Reported Outcome Measurement Information System (PROMIS) 29
 
	
IV	3 months	-Perineal pain score (VRS)	

Information will be collected remotely via electronic and/or printed surveys, depending on the patient's preference		
 
-Need for additional analgesic intake for management of perineal pain (yes or no) 
 
• Total analgesic consumption (opiates/nsaids)
 
 
 
-Physical therapy treatment (yes or no)
 
-The McGill Pain Questionnaire
 
-Brief Pain Inventory (BPI) Short Form
 
- If plan was to breastfeed, is patient currently breastfeeding? yes or no? If not, why did she stop?
 
-Edinburgh Postnatal Depression Scale (EPDS)
 
-Maternal Postnatal Attachment Scale (MPAS)
 
-Patient Reported Outcome Measurement Information System (PROMIS) 29
 
- Female Sexual Function Index (FSFI)
 
	
V	6 Months	
 
-Perineal pain score (VRS)
 
-Physical therapy treatment for pelvic pain (yes or no)
 
- If plan was to breastfeed, is patient currently breastfeeding? yes or no? If not, why did she stop? -
 
Patient Reported Outcome Measurement Information System (PROMIS) 29
 
- Female Sexual Function Index (FSFI)
 
	
VI	12 Months	
 
-Perineal pain score (VRS)
 
-Physical therapy treatment for pelvic pain(yes or no)
 
- If plan was to breastfeed, is patient currently breastfeeding? yes or no? If not, why did she stop?
 
	

		-Patient Reported Outcome Measurement Information System (PROMIS) 29 - Female Sexual Function Index (FSFI)	
--	--	---	--

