#### **DATA AND SPECIMEN BANKING: N/A**

#### **DATA AND SPECIMEN MANAGEMENT:**

The primary outcome of this study is the proportion of women with pain (VRS > 4, on a 0 to 10 scale) with activity at 7±3 days postpartum. Based on the study of Macarthur et.al evaluating pain following perineal injury following childbirth, we estimated that 55% of women would have pain (VRS > 4, on a 0 to 10 scale) at 7 days. We assumed an absolute reduction of 25% in pain in women receiving epidural morphine 3mg + intravenous saline compared to epidural saline +

intravenous saline, and an absolute reduction of 30% in pain in women receiving epidural morphine 3mg + intravenous ketamine 0.3 mg/kg compared to epidural saline + intravenous saline. Groups sizes of 30:60:60 will be required to detect a difference in an effect size of 0.25 (Cramér's  $\omega$ ) at a power of 0.8 and an alpha of 0.05 using  $\chi^2$  statistic. A sample of 150 subjects will be randomized using a 1:2:2 randomization to epidural saline plus intravenous saline, epidural morphine + intravenous saline, and epidural morphine + intravenous ketamine groups. We will recruit up to 160 patients to account for subjects that decline participation and lost to follow-up.

The completed data forms will be kept in folders with only the study ID number as an identifier. These folders will be placed in a secure, locked cabinet in the Office of the Section of Obstetrical Anesthesiology located in Prentice Women's Hospital 9th floor. REDcap will be used for data entry. Only study team members will have access to the data files. Data will be password protected using a Department of Anesthesiology dedicated computer which is backed up nightly by the departmental server which is located on the 5th floor Arkes Pavilion. The access is controlled by key card and password protected by the departmental data manager.

Only the study ID number will be used to identify participants during data analysis. The data will be stored in the departmental computer until the completion of the study, including the final data analysis. Members of the anesthesia team collecting these data will be educated on the process prior to approaching prospective participants. Data both electronic and paper will be destroyed 5 years after the study has been completed using current standards and vendors.

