The Asher Center for the Study and Treatment of Depressive Disorders, directed by [name] MS, is a clinical research women's mental health program at Northwestern's Department of Psychiatry and Behavioral Sciences. [name] holds academic appointments in the Departments of Psychiatry and Behavioral Sciences and Obstetrics and Gynecology. The Asher Center includes 10,000 square feet of research space which accommodates investigators and staff performing and mental health evaluations and research. This space is integrated with a 5,000 square foot clinical care program staffed by an interdisciplinary team of psychiatrists, psychologists, a maternal-fetal medicine research scholar, nurses, and trainees. The Asher Center is located one block from Prentice Women's Hospital. The Asher Center includes two examination rooms specifically furnished with space for examination of mothers and infants, with digital weight scales accurate to .01 g. Two conference rooms (for 12 or 30 people) with audiovisual equipment are available for staff meetings and for other work-related functions. The family room includes comfortable sofas, rocking chairs, and toys for children of all ages. The Center has diaper changes and waste containers in all restrooms. Quiet rooms for breastfeeding women and a kitchen with sink, refrigerator, microwave and snacks are also available.

[name] and Asher Center staff will provide consultation regarding use of the depression assessments and interpretation of depression measures and data, as well as participate in manuscript development. Our resources will be utilized for emergent psychiatric situations that may arise, such as suicidality.

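### The 1-week and 6-week depression endpoints are a yes/no presence with no EPDS cut-off or analysis stated; make the EPDS total score the main comparison and fix one cut-off in advance as support

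*Combined protocol and SAP*

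**What the plan says.** The Study Endpoints section of the combined protocol and SAP names two secondary depression endpoints: "Presence of postpartum depression within 1 week after delivery" and "presence of postpartum depression 6 weeks after delivery". Both are worded as yes/no. That section names no instrument.

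The link to an instrument comes from the Study timeline table, which schedules the EPDS at PPD 2-7, 6 weeks and 3 months and lists no other depression measure. The PPD 2-7 row also gives the reasoning: "if perineal pain is not well –controlled, the patient will be at increased risk for depression". No cut-off or scoring rule appears there or elsewhere. Under Resources Available, specialist staff "will provide consultation regarding use of the depression assessments and interpretation of depression measures and data", but no rule is recorded.

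The primary outcome is treated differently. Data and Specimen Management gives its cut-off: "The primary outcome of this study is the proportion of women with pain (VRS > 4, on a 0 to 10 scale", assessed with activity about a week after delivery. It also gives an assumed control rate ("we estimated that 55% of women would have pain"), a test and a sample size. Nothing comparable exists for depression. The χ² test is named for the primary outcome, and χ² or Fisher's exact test for the safety review. No test is named for any secondary efficacy endpoint.

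**The concern.** Two things follow from a yes/no endpoint on a scored scale with no cut-off.

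First, two analysts working from this plan could not be sure of computing the same endpoint. A cut-off settled after the data are seen also cannot be shown to be independent of the results.

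Second, splitting a score into two categories discards information. The arms are planned at 30, 60 and 60, so if few women score above the cut-off the comparison rests on a handful of cases.

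This matters because the Background offers an antidepressant effect as one reason for including ketamine. A weak analysis of depression could miss an effect that the trial was partly designed to look for, although the scores that would support a better analysis are already being collected.

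**Working it through.** **The plan's own figure.** Data and Specimen Management gives effect size w = 0.25, alpha 0.05 and N = 150 at 30:60:60. A χ² test of three arms by two outcomes has 2 df and critical value 5.99.
- Noncentrality: λ = N·w² = 150 × 0.0625 = 9.375, which gives power 0.788.
- Power of exactly 0.80 needs N of about 154.

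The plan's 150 and 0.80 are thus reproduced closely. The same three-arm test is used for the yes/no outcome below. No power figure is stated for depression.

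**Inputs for depression.** Only the arm sizes (shares 0.2, 0.4, 0.4 of 150) come from the documents. The rest is assumed: a normal score with SD 1, a downward shift of d SD in the arms that benefit, and a saline-arm rate P. P fixes the cut-off at z = Φ⁻¹(1 − P), so the rate in a shifted arm is 1 − Φ(z + d). All 150 women are taken to have data.

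**Total score.** λ = N·Σ share × (mean − overall mean)², tested by F on 2 and 147 df (critical value 3.06).
- Both morphine arms shift by 0.5: means 0, −0.5, −0.5; overall −0.4. λ = 150 × (0.2 × 0.16 + 0.8 × 0.01) = 6.0, power 0.575.
- Only the ketamine arm shifts by 0.5: overall mean −0.2. λ = 150 × (0.6 × 0.04 + 0.4 × 0.09) = 9.0, power 0.76.

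**Yes/no.** λ = N·Σ share × (p − p̄)² / [p̄(1 − p̄)], tested by χ² on 2 df. Example for P = 10% with both morphine arms shifted by 0.5:
- z = 1.282, shifted rate 1 − Φ(1.782) = 0.0374.
- p̄ = 0.2 × 0.10 + 0.8 × 0.0374 = 0.0499.
- λ = 150 × (0.2 × 0.0501² + 0.8 × 0.0125²) / (0.0499 × 0.9501) = 1.98, power 0.224.
- Expected positives are 3, 2.2 and 2.2, about 7 women in 150.

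Loss is 1 minus the ratio of yes/no power to score power:

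| Saline rate | Yes/no power, both arms shift (score 0.575) | Loss | Yes/no power, ketamine arm only (score 0.76) | Loss |
|---|---|---|---|---|
| 10% | 0.22 | 61% | 0.23 | 70% |
| 15% | 0.28 | 52% | 0.30 | 61% |
| 20% | 0.32 | 45% | 0.35 | 54% |
| 25% | 0.35 | 40% | 0.40 | 48% |
| 50% | 0.41 | 30% | 0.54 | about 30% |

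**Other assumptions, both morphine arms shifted.**
- 0.8 SD: score 0.945; yes/no 0.48 to 0.73 at rates of 10 to 25%, a loss of 49% down to 23%.
- 0.3 SD: score 0.24; yes/no 0.11 to 0.15 at the same rates.

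**Skewed score.** This was a simulation of saline against one active arm (30 v 60), with a negative binomial score of size 4 capped at 30 and 2,000 runs. With means of 7 v 5, the t test has power 0.60 and the rank test 0.59. Yes/no has 0.48 when the control rate is 24% and 0.34 when it is 11%. The losses against the t test are 20% and 44%. With larger mean differences (7 v 4.5 and 7 v 4) they are 16 to 36%.

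**Open cut-off.** In 20,000 null simulations at 30:60:60, cut-offs were set at 25, 15 and 10% positive. The false-positive rate is 0.05 for one fixed cut-off, about 0.08 for the better of two and about 0.11 for the best of three.

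**The case against.** The strongest reply is that the documented gap is a missing cut-off, and one sentence would close it. That sentence would remove the free choice and with it the 0.11. This stands as far as it goes. It would still leave a yes/no comparison with less power than the score in every scenario tried.

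A second reply is that presence of depression and mean score are different questions: a shift among women with low scores does not mean fewer depressed women. This stands too, and is why the proportion should be kept as a supportive result and not reduced to description only.

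Third, the trial was sized for the primary outcome alone, so low power for a secondary endpoint is expected and is not an error in the plan. The score does not cure it: its power is 0.58 at a 0.5 SD shift in both morphine arms and 0.24 at 0.3 SD. The argument is only that the score makes better use of data already collected.

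Fourth, the missing analysis is not peculiar to depression, since no secondary efficacy endpoint has a named test. That is true. Depression stands out because its wording also imposes a split without saying where.

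A reader might go further and infer that the plan throws away half its power, or that cut-offs will be tried until one works. The documents support neither. They contain no depression rate, EPDS standard deviation or effect from which a single loss could be derived. Nothing in them suggests that several cut-offs will be tested, and they provide for specialist advice on interpretation.

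**Conclusion.** The point holds as a cheap improvement to two secondary endpoints. From the documents alone, depression at 1 week and 6 weeks is worded as yes/no, the only scheduled depression measure is a scored scale, and neither a cut-off nor an analysis is given.

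The size is conditional. Under a normal score with a 0.5 SD shift in both morphine arms, the yes/no form loses about 40 to 60% of the score's power at saline rates of 10 to 25%, and about 30% at a rate of 50%. The loss is larger if only the ketamine arm shifts and rates are 10 to 25%, and smaller for a larger shift. For the skewed scores tried it is roughly 16 to 44%. That yes/no has less power is consistent across these scenarios; no single percentage is. The 0.11 false-positive rate shows what an open cut-off permits, not what is expected to happen.

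**What to change.** In Study Endpoints, name the EPDS and make the between-arm comparison of its total score the main analysis of depression at 1 week and at 6 weeks. Use a linear model, or a rank test if scores are clearly skewed, and state in advance how that choice will be made. Keep the proportion above one EPDS cut-off as a supportive result, with the cut-off written into the plan before unblinding.

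The cost is protocol wording: no new visits, instruments or participants. The small downside is that a score difference is less direct to read than presence and answers a slightly different question, which is why the proportion is still reported.
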